TUFTS MEDICAL CENTER/TUFTS UNIVERSITY RESEARCH PROTOCOL

Version date: 07/23/2018

ClinicalTrials.gov ID NCT02811445

Study Title: Role of the gut microbiome and the serum metabolome on lean mass and physical function in older adults

Principal Investigator: [name]

Co-Investigator: [name].
[name].

Study Doctor/Co-Investigator: [name].

Study Coordinators: [name]
[name]

I. Research Plan

40 older adults (70-85y) will be recruited from the local Boston area based on their performance on the short physical performance battery (SPPB), a measure of lower extremity physical function that includes standing balance, a 4-m walk and chair stand tests^[1]. The SPPB has been extensively validated as predictive of future disability risk and mortality in older adults^[1]. High-functioning (HF; SPPB ≥ 11) and low-functioning (LF; SPPB ≤ 8)^[2] groups will each contain 20 subjects (10 men, 10 women). Gut microbial composition is affected by age^[3, 4]. Similarly, sex and BMI are associated with gut microbiome composition^[5-7]. With the goal of minimizing gut microbial variability, I propose to recruit HF and LF subjects that are matched for age, sex and BMI but are different in terms of lean mass and physical function.

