Transplantation of gut microbiota from a healthy human adult into germ-free mice resulted in all bacterial phyla, 92% of bacterial classes and 88% of genus-level taxa being detected in the feces of recipient germ-free mice^[37]. Human gut bacteria-containing mice fed a high-fat western diet gained significantly more adiposity during the two weeks following transplantation than mice that consumed a low-fat, plant polysaccharide-rich diet^[37], evidence that demonstrates a causative role for diet-induced increases in adiposity by human gut bacteria. Similarly, transplantation of human gut microbiota from 3 twins (2 female and 1 male) discordant for obesity into germ-free mice resulted in ~75% of family-level bacterial taxa and 99.7% of the functions encoded by the donor's microbiome being represented in recipient mice, thereby resulting in a greater increase in adiposity in mice colonized with fecal microbiota from obese, when compared with its lean co-twin^[38].

Collectively, these studies demonstrate that transfer of gut bacteria from humans into germ-free mice is highly efficient, functions encoded by the transferred microbiome are maintained, and phenotypes are transmissible. The objective of **AIM 2** is to test the causative role of human gut bacteria on the maintenance of lean mass and physical function by transferring fecal microbiota from HF and LF older adults into germ-free mice.

Statistical Power: Germ-free mice colonized with fecal bacteria from obese humans gained significantly more adiposity than germ-free mice colonized with fecal bacteria from their lean co-twin ($10.0\% \pm 5.0\%$ compared with $0.1\% \pm 2.0\%$), a result that was significant 15 days after colonization^[38]. Based on these data, the resulting effect size of 2.6 is sufficient to obtain 99% power at a type-I error probability of 0.05 with a sample size of 12 human subjects. Accordingly, with the goal of identifying a similar change in lean mass and physical function, I propose to transfer fecal bacteria from 12 older adults into germ-free mice.

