- iii) BMI: males < 35, females <30 kg/m²
- iv) Willing to come to the HNRCA laboratory for baseline and 1-month follow-up study visits
- v) SPPB ≥ 11 (“High-Functioning”, HF; 20 subjects: 10 males, 10 females)
- vi) 4 ≤ SPPB ≤ 8 (“Low-Functioning”, LF; 20 subjects: 10 males, 10 females)

b) Exclusion Criteria:

- i) Non-English speaker
- ii) Acute or terminal illness
- iii) Surgery in the past 6 months
- iv) Lower extremity fracture within the past 6 months
- v) Myocardial infarction in the past 6 months
- vi) Coronary artery disease, peripheral vascular disease, previous stroke, or history of transient ischemic attacks
- vii) Cognitive impairment (MMSE score < 23)
- viii) Uncontrolled hypertension (> 160/100 mmHg)
- ix) Neuromuscular disease or drugs affecting neuromuscular function
- x) Androgen therapy in males
- xi) Estrogen therapy in females

- xii) Significant immune disorder
- xiii) Kidney Failure
- xiv) Pancreatic disease
- xv) Diabetes
- xvi) Gastrointestinal or malabsorption diseases
- xvii) History of cholecystectomy
- xviii) Use of probiotics, prebiotics or antibiotics in the past 3 months
- xix) The subject has any other condition, which in the opinion of the Investigator, precludes the subject's participation in the trial.
- xx) With the goal of matching the HF and LF groups for age, sex, and BMI, subjects may be excluded because their age, sex or BMI puts them outside the range needed for this study.

c) **Withdrawal/Termination criteria:** Subjects may stop participating in this study at any time for any reason. If an enrolled subject decides to withdraw from this research study, they will be asked to inform the Principal Investigator ([name]), the Lab Director ([name]), or his representative. The principal investigator may stop participation in this research study without the subject's permission for any of the following reasons:

- The participant did not adhere to any or all HNRCA volunteer rules and regulations
- Participant does not follow the study procedures
- There has been a change in the subject's health that would make the subject ineligible

B. Risk/benefit assessment:

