 - v) *Stool Collection:* Stool samples will be obtained at the baseline and 1-month study visits. Stool samples will be collected (see Supplementary documents) and stored as specified in the Manual of Procedures by the Human Microbiome Project^[46]. Freshly obtained stool samples will be transported to the Phoenix Laboratory at Tufts Medical Center, where the stool samples will be homogenized, aliquotted into ten 200mg lots into pyrogen-free Eppendorf tubes, and frozen at -80°C. Five additional 200 mg aliquots will also be saved for future exploratory analyses, which may include additional gut bacterial profiling. Consent for tissue storage will be obtained through a separate consent form. Subjects who initially consent to tissue banking but later decide to withdraw their stool samples from

storage and future use may sign and return a section of the consent form pertaining to this or verbally notify the Principal Investigator or study coordinator at any time.

vi) *DXA*: Total body lean mass will be measured at baseline and 1-month follow-up visits using DXA (Discovery A, Hologic Inc., Waltham, MA) at the Boston Nutrition Obesity Research Center Body Composition Unit at Tufts University. The DXA system generates photons at two principal energy levels (40 and 70 KeV) which allow measurement of bone mineral and soft tissue. Lower extremity skeletal muscle mass will be estimated using the DEXA-SM model developed by Wang *et al.* (1999)^[47]. The reliability of this method for estimating regional skeletal muscle mass is high (C.V. < 4%).

vii) *Measurement of Dietary Intake*: If you are enrolled into the study you will complete 3 record-assisted, 24-hour dietary recalls. A member of the Tufts University Dietary Assessment Unit will provide instructions and a log, and will ask you to write down everything you eat and drink over the 24-hr period during the 2 days prior to your baseline visit. The final dietary recall will be completed in-person at the baseline visit, for a total of three 24-hour dietary recalls. You will be given a two-dimensional measuring aid (Food Amounts Booklet) to assist with estimating portion size. A member of the Dietary Assessment Unit will complete dietary recalls by phone with you over the two days prior, and including on the day of your baseline visit.

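### Matching HF and LF on BMI while expecting a lean-mass difference tends to leave LF with more fat, and no stated human analysis includes fat mass or height

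*Protocol*

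**What the plan says.** The Research Plan, identical on this point in the protocol and the SAP, selects subjects "based on their performance on the short physical performance battery (SPPB"). It then states: "I propose to recruit HF and LF subjects that are matched for age, sex and BMI but are different in terms of lean mass", with function as the other intended difference. BMI is on the matching list because "sex and BMI are associated with gut microbiome composition".

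Matching works by exclusion. The last exclusion criterion (Protocol, A.1.b) reads "With the goal of matching the HF and LF groups for age, sex, and BMI, subjects may be excluded because their age, sex or BMI" falls outside the needed range. No BMI tolerance and no pairing are stated, and height is not a matching factor. The BMI limits are wide: "BMI: males < 35, females <30 kg/m²", with no lower limit.

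On body composition, Protocol C.1.vi says "Total body lean mass will be measured at baseline and 1-month follow-up visits using DXA". Leg muscle mass is also estimated. Fat mass is not listed, and lean mass is not indexed to height.

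The human group tests (Aim 1) are analysis of similarities on UniFrac distances and LEfSe. No covariate is named for either. Associations with lean mass as a continuous measure are planned separately, again with no stated adjustment for fat or height.

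In the Aim 2 background, the protocol describes transplantation from twins discordant for obesity as "resulting in a greater increase in adiposity in mice colonized with fecal microbiota from obese, when compared with its lean co-twin".

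**The concern.** BMI is matched to remove a body-size influence on the microbiome. BMI does not distinguish lean from fat, however. If LF has less lean mass at the same BMI, the difference tends to be made up by fat. The matching then leaves an adiposity contrast lying along the HF/LF contrast.

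A taxon or metabolite that follows body fat could then be credited to lean-mass maintenance. The 1-month repeat would not expose this. It re-tests the same people, and a body-composition difference would be expected to persist over a month. The contrast may also carry into Aim 2, where the donors are 6 HF and 6 LF subjects with no stated selection on body composition. The mouse outcomes are lean mass, grip strength and swimming endurance, and fat is not listed among them.

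**Working it through.** **The plan's own figures.** The documents give no figure for fat. The Aim 1 effect size reproduces: (26.3 − 14.8)/√[(13.2² + 15.1²)/2] = 11.5/14.18 = 0.81. This point does not depend on it. The Aim 2 effect size also reproduces: (10.0 − 0.1)/√[(5.0² + 2.0²)/2] = 9.9/3.81 = 2.60. That one is an adiposity effect, so the only mouse phenotype the protocol quantifies is one the plan does not list as an outcome.

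**Identity.** Fat = BMI × height² − lean − bone. With equal BMI and equal bone, the HF minus LF difference is approximately

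Δfat = −Δlean + BMI × Δ(height²).

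- Equal height: a lean difference of +1, +2 or +3 kg gives a fat difference of −1, −2 or −3 kg.
- Unequal height: Δfat is zero for a 2 kg lean difference when BMI × Δ(height²) = 2. At an assumed BMI of 30 and height of 1.75 m, HF must be √(1.75² + 2/30) − 1.75 = 1.9 cm taller. At BMI 24 and 1.60 m, it is √(1.60² + 2/24) − 1.60 = 2.6 cm.
- Chance height gap: with an assumed within-sex SD of 5-7 cm, the SE of the mean difference at 20 v 20 is SD × √(2/20) = 1.6-2.2 cm.
- Imperfect BMI match: 2 kg corresponds to 2/1.75² = 0.65 to 2/1.60² = 0.78 kg/m².

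**How often the opposite fat gap appears.** I simulated 20 v 20 with the same BMI distribution in both groups (SD 2-4), within-sex height SD 6.5 cm, fat-fraction SD 0.04-0.06, and a lean gain built in for HF at fixed BMI. All of these inputs are assumptions. The mean fat difference mirrored the lean difference.

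| Built-in lean gain in HF | Samples with lower HF fat, given higher HF lean |
|---|---|
| 1 kg | 65-77% |
| 2 kg | 84-93% |
| 3 kg | 93-98% |

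**Effect on a purely fat-related taxon.** Assumptions: lean-index gap 0.5-1.0 kg/m² (1.4-2.8 kg at 1.67 m), fat-index SD 2.0-2.5 kg/m², taxon-fat correlation r = 0.4-0.6. Shift = r × gap/SD.

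| Gap, kg/m² | Shift, SD units | Rejection at 20 v 20, two-sided 5% (noncentral t) |
|---|---|---|
| 0.5 | 0.4 × 0.20 = 0.08 to 0.6 × 0.25 = 0.15 | 5.7% to 7.5% |
| 1.0 | 0.4 × 0.40 = 0.16 to 0.6 × 0.50 = 0.30 | 7.8% to 15.2% |

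These are rates per taxon for a t test, used here as a guide to what LEfSe would do.

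**Continuous lean mass.** Across the 40 simulated subjects, the correlation of absolute lean with absolute fat given sex ran from −0.25 to +0.51, because larger people tend to have more of both. Variance inflation with both in the model was only 1.0-1.4. For height-indexed lean and fat given BMI, the correlation was −1.00.

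**Donors.** With a fat gap of 0.4-0.5 SD and 6 v 6 independent donors, LF averages fatter with probability Φ(0.4/√(2/6)) = 76% to Φ(0.5/√(2/6)) = 81%. With half that gap it is 64-67%.

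**The case against.** A reader might infer that BMI matching forces an opposite fat difference, so that lean-mass bacteria cannot be told from adiposity bacteria. The documents do not support that.

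- The identity is exact only for height-indexed lean mass or equal height. The planned measure is absolute, height is unmatched and the BMI match has no stated tolerance. Groups are set by SPPB, so the lean difference is expected, not imposed. A height gap of about 2 cm, which is within chance, absorbs 2 kg of lean. This objection stands: the fat gap is a tendency. But such offsets are accidents, not controls, and the plan states no check for them.
- Matching constrains group averages, not individuals. With variance inflation of 1.0-1.4, absolute lean and fat can be separated once fat is analysed. This also stands. It makes the remedy feasible, but the plan as written does not use it.
- One might expect a fat-linked taxon to associate inversely with lean mass. That extends a group-mean relation to individuals, where the lean-fat correlation can take either sign.
- One might expect such a taxon to separate HF from LF. Under the assumptions above, at least about 85% of tests of purely fat-related taxa would not flag it.
- Adjusting HF/LF for fat at matched BMI takes out much of the lean contrast itself. This stands and limits the remedy.
- The protocol calls the study a pilot. That bears on how much machinery to add, but not on whether fat should be reported.

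**Conclusion.** The concern holds as a matter of open confounding. BMI matching combined with an expected lean-mass difference tends to give LF more fat, and no stated human test or association includes fat mass or height. This is judged on the text available. Section III.1.b, cited for the association method, does not appear under that number.

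The size is modest: from 5% to about 6-15% per fat-related taxon at 20 v 20, conditional on the assumed lean gap, fat SD and correlation, none of which the documents give. For continuous absolute lean mass, neither the sign nor the size of the bias can be fixed in advance. It is likely, but not assured, that LF donors would be the fatter ones: 64-81% under the same assumptions. The issue matters mainly because the study's central attribution is to lean mass, and the protocol's own example of a transmissible phenotype is adiposity.

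**What to change.** 1. Derive fat mass from the existing DXA scan, or as weight minus lean minus bone. Report fat mass and height by HF/LF group and for the 6 v 6 donors.
2. In the lean-mass associations, enter absolute lean mass together with fat mass and height, adjusted for sex. Do not fit indexed lean, indexed fat and BMI in the same model.
3. Keep analysis of similarities and LEfSe as the main HF/LF tests. Add a fat-adjusted sensitivity analysis using a method that accepts covariates.
4. Describe a feature as lean-mass-related, as opposed to body-composition-related, only with the fat-adjusted estimate shown beside it.
5. In mice, report fat beside lean mass if the body-composition scan provides it.

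Cost: SAP wording and one additional covariate-capable analysis. No new scan is needed, assuming the DXA output gives fat, or lean and bone so that fat follows by subtraction. Some precision is lost at n = 40. Because adjusting the HF/LF contrast for fat also removes part of the lean contrast, that analysis should inform interpretation and not act as a condition for reporting a finding.

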At baseline, subjects will provide a blood and stool sample that will be subjected to serum metabolomics and fecal sample 16S ribosomal RNA (16S rRNA) gene profiling, respectively. Serum metabolomics provides an analytical description of complex biological media by identifying a large number of small molecule metabolites in a given biological sample^[8]. Fecal sample 16S rRNA gene profiling will be used to identify the bacterial relative abundance that is present within each taxonomic level in each fecal sample. Lean mass and physical function will be measured in all subjects. Associations between serum metabolites, fecal bacteria, and between fecal bacteria and serum metabolites with the differentiation of HF from LF, and that are associated with lean mass and specific measures of physical function will be determined. In addition, associations between gut bacteria with circulating markers of insulin resistance and endotoxemia will be identified. Overlapping associations between gut bacteria and serum metabolites with these outcomes is expected to provide an enhanced understanding about the role of gut bacteria on mechanisms that underlie the maintenance of lean mass and physical function in older adults. The causative role of gut bacteria on the maintenance of lean mass and physical function in older adults will be examined by transplanting fecal bacteria from older adults into germ-free mice.

After 1 month, to determine the reproducibility of the baseline gut bacterial associations with lean mass and physical function, study subjects will return to provide a fecal sample that will be subjected to 16S rRNA profiling. Lean mass and physical function will be measured, and associations between fecal bacteria that collectively differentiate HF from LF, and that are associated with lean mass and specific measures of physical function will be identified and compared with baseline findings.

Statistical power: Sample size estimates are based on gut bacterial associations with the GFI^[9]. Means \pm SD for *Bacteroides/Prevotella* of 26.3 ± 13.2 and 14.8 ± 15.1 in the low-frailty and high-frailty groups, respectively, yield an effect size of 0.81, a value that is sufficient to obtain 80% power at a type-I error probability of 0.05 with a study sample size of 40 subjects. To achieve this recruitment goal, up to 150 subjects will sign the Preadmission ICF, with the goal of 40 participants completing the study.

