Bacterial taxa that differentiate HF from LF older adults: Principal co-ordinate analysis (PCoA) of the phylogeny based Unifrac distance metric^[32], which are derived from OTUs^[33] will be used to determine if the overall gut microbial profile in HF is significantly different when compared with LF older adults. The analysis of similarities function in the statistical software package PRIMER 6 (PRIMER-E Ltd., Lutton, UK^[34]) will be used to determine between-group statistical significance ($p \leq 0.05$). To identify bacterial taxa and relative abundance that are significantly different in HF when compared with LF older adults, linear discriminant analysis effect size (LEFSE)^[35] will be used. LEFSE is an algorithm for high-dimensional biomarker discovery and explanation that identifies bacterial taxa that characterize the difference between two or more biological conditions.

Test the causative role of human gut bacteria on the maintenance of lean mass and physical function: Although identification of gut bacteria that are associated with lean mass and physical function is an important observation, transplanting intact uncultured human fecal microbiota into recipient germ-free mice permits the donors' communities to be replicated and the causative role of their microbiota on outcome measures to be

discerned. For example, transplantation of human gut microbiota from 4 female twins discordant for kwashiorkor (the condition caused by severe dietary protein deficiency) into germ-free mice resulted in 86-90% of species-level taxa and ~90% of the functions encoded by the donor's microbiome being found in recipient mice, thereby implicating the gut microbiota as a causal factor on kwashiorkor^[36].

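### The 80% power belongs to one unadjusted Bacteroides/Prevotella comparison that the plan never specifies; its taxa enter only as unnamed members of an all-taxa LEFSE screen

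*Protocol*

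**What the plan says.** The text is the same in the protocol and the SAP.

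- **Sizing** (section I, Statistical power). "Sample size estimates are based on gut bacterial associations with the GFI". The planning values are means and SDs for Bacteroides/Prevotella "of 26.3 ± 13.2 and 14.8 ± 15.1 in the low-frailty and high-frailty groups"; these "yield an effect size of 0.81", said to give "80% power at a type-I error probability of 0.05 with a study sample size of 40 subjects". Sidedness and the type of test are not stated. Section I sets 20 subjects per group, and the 40 are completers: "with the goal of 40 participants completing the study".
- **Whole-community test** (Aim 1, paragraph on taxa that differentiate HF from LF). Principal co-ordinate analysis of UniFrac distances "will be used to determine if the overall gut microbial profile in HF is significantly different when compared with LF older adults", with analysis of similarities at p ≤ 0.05.
- **Taxon-level search** (same paragraph). "To identify bacterial taxa and relative abundance that are significantly different in HF when compared with LF older adults", LEFSE is used. No taxon is named, and no significance level, effect cut-off or multiplicity rule is given for LEFSE. The preceding Aim 1 paragraph profiles relative abundance at every taxonomic level.

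Bacteroides/Prevotella appears in neither document outside the power paragraph.

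**The concern.** A power figure is useful only if it can be attached to a test that will be run. Here it is computed for one variable, tested once at 0.05, taken from an external frailty study that supplies a direction and a size. The analysis section then neither names that variable nor gives it a test.

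Two consequences follow. If the screen does not flag Bacteroides or Prevotella, that absence cannot be read against 80% power, because the screen was not what was powered. If the screen does flag them, the finding is one hit among many with no protected error rate. The study would then report no error-controlled taxon result, although it was sized as if it would have one.

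**Working it through.** **Inputs from the documents.** Means 26.3 and 14.8; SDs 13.2 and 15.1; n = 20 per group; alpha 0.05.

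**1. Effect size.** Difference = 26.3 − 14.8 = 11.5. Pooled SD = √[(13.2² + 15.1²)/2] = √[(174.24 + 228.01)/2] = √201.125 = 14.18. d = 11.5/14.18 = 0.811. This reproduces the stated 0.81.

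**2. Stated power.** Two-sample t-test with 38 degrees of freedom and noncentrality d√(n/2) = 0.811 × √10 = 2.564:

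| Test at 0.05, 20 v 20 | Critical t | Power | n per group for 80% |
|---|---|---|---|
| One-sided t | 1.686 | 80.9% | 20 |
| Two-sided t | 2.024 | 70.5% | 25 |

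The normal approximation gives 82.1% one-sided and 72.7% two-sided. The stated 80% with 40 subjects is thus the power of a single one-sided two-sample t-test on one variable.

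**3. Match to the planned analyses.**

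| Planned HF v LF analysis | What is tested | Is it the powered comparison? |
|---|---|---|
| Analysis of similarities on UniFrac | One hypothesis about the whole community | No; d for one taxon group does not determine its power |
| LEFSE | Every taxon, none named, level not stated | No; Bacteroides and Prevotella are unnamed members |

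The documents do not say whether Bacteroides/Prevotella is a combined group or a ratio. If it is either, LEFSE applied to the component taxa would not test the quantity used for sizing.

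**4. Power if the comparison were named.** The high-frailty SD (15.1) exceeds its mean (14.8), which for a non-negative abundance implies skew, so a rank test is the natural choice. Simulated power of an unstratified two-sided Wilcoxon test at 0.05, with the stated means and SDs (20,000 runs):

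- normal data: about 67%;
- gamma data: about 87%.

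Stratifying by sex (two strata of 10 v 10, no sex effect assumed) leaves these almost unchanged. The two shapes are assumptions, not bounds: a beta shape, if the values are percentages, gives 82%, and a lognormal shape 94%.

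**5. Inside a screen (illustration only).** With m taxa and a Bonferroni two-sided t-test, alpha = 0.05/m. For m = 10, alpha = 0.005 and power is 35%; for m = 100, alpha = 0.0005 and power is 13%. With no correction, the chance of at least one false positive among m independent null taxa is 1 − 0.95^m: 40% for m = 10 and 99% for m = 100. Both m and the correction are assumed; the plan gives neither.

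**The case against.** **LEFSE does compare taxa between HF and LF.** This stands. A reader might infer that Bacteroides and Prevotella are never compared between the groups. The documents do not support that: the screen covers all taxonomic levels, so these taxa are examined in it. What is missing is a named, single comparison to which the power figure could apply.

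**No multiplicity correction is stated.** This also stands. A reader might infer from step 5 that the study's true power for this taxon is 35% or 13%. Those figures need a taxon count and a Bonferroni rule that the plan does not contain. Equally, it cannot be asserted that the taxon would be judged at a level other than 0.05 within LEFSE; the level is simply not given.

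**The study is exploratory.** Aim 1 seeks to identify and characterise associations, and the safety monitoring section calls the study a pilot. Borrowing one published effect as a planning value is common in discovery work. The sizing source also used a frailty index that Aim 1 itself regards as not specific to physical function, whereas the groups here are defined by SPPB. These points weaken any claim that a confirmatory taxon result was promised, and they make dropping the power claim an acceptable alternative. They do not remove the mismatch, because the plan still makes a formal 80% claim.

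**Naming a test does not make the 80% right.** Correct. The figure cannot be transferred to a two-sided Wilcoxon test, whose power depends on the assumed distribution.

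**Conclusion.** The concern holds in this form: the study is sized for one unadjusted Bacteroides/Prevotella comparison at 0.05, the plan specifies no such test, and the stated 80% therefore describes neither the analysis of similarities nor the LEFSE screen. The effect size is reproduced from the plan's own inputs, and the 80% only on a one-sided reading of the t-test. As a named two-sided test with 20 v 20, the comparison has 71% power by t-test and roughly 67% to 87% by Wilcoxon, the upper figure resting on an assumed gamma shape.

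The finding does not establish that the trial is underpowered for its actual analyses, since the documents give too little to compute their power. It is a correction that should be made because it is cheap and decides how a positive or null taxon result can be read.

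**What to change.** **Aim 1, paragraph on taxa that differentiate HF from LF (protocol and SAP).** Before any HF/LF taxon results are seen, add text to this effect:

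> One taxon comparison is pre-specified: Bacteroides/Prevotella at baseline, HF v LF, defined as in the sizing source [state whether combined group or ratio, and units]. It is tested once, outside the LEFSE screen, by a two-sided Wilcoxon test stratified by sex at alpha 0.05. All other taxon results are exploratory.

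**Section I, Statistical power (protocol and SAP).** Say that the calculation refers to this test and replace the 80% with its power, giving the distributional assumption: with 20 v 20 and d = 0.81, about 67% (normal) to 87% (gamma) for the unstratified two-sided Wilcoxon test, with 71% for a two-sided t-test as reference.

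**If HF/LF taxon results have already been seen,** naming the comparison now would be post hoc. In that case delete the power claim and describe N=40 as a pilot size. Both documents are written in the future tense and do not settle this, so the sponsor should state it.

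**Cost.** Wording only; no extra samples or visits. The price is that other taxa are openly exploratory and that the stated power is less favourable under a t-test or normal data. Restoring 80% under a two-sided t-test would take 25 per group (N=50), a separate decision that this change does not require.

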Bacterial taxa that differentiate HF from LF older adults: Principal co-ordinate analysis (PCoA) of the phylogeny based Unifrac distance metric^[32], which are derived from OTUs^[33] will be used to determine if the overall gut microbial profile in HF is significantly different when compared with LF older adults. The analysis of similarities function in the statistical software package PRIMER 6 (PRIMER-E Ltd., Lutton, UK^[34]) will be used to determine between-group statistical significance ($p \leq 0.05$). To identify bacterial taxa and relative abundance that are significantly different in HF when compared with LF older adults, linear discriminant analysis effect size (LEFSE)^[35] will be used. LEFSE is an algorithm for high-dimensional biomarker discovery and explanation that identifies bacterial taxa that characterize the difference between two or more biological conditions.

Test the causative role of human gut bacteria on the maintenance of lean mass and physical function: Although identification of gut bacteria that are associated with lean mass and physical function is an important observation, transplanting intact uncultured human fecal microbiota into recipient germ-free mice permits the donors' communities to be replicated and the causative role of their microbiota on outcome measures to be

discerned. For example, transplantation of human gut microbiota from 4 female twins discordant for kwashiorkor (the condition caused by severe dietary protein deficiency) into germ-free mice resulted in 86-90% of species-level taxa and ~90% of the functions encoded by the donor's microbiome being found in recipient mice, thereby implicating the gut microbiota as a causal factor on kwashiorkor^[36].

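### The 80% power stated for 40 subjects holds only for an undeclared one-sided test; for the non-directional HF/LF comparisons planned, the two-sided figure is about 70%

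*Protocol*

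**What the plan says.** The power paragraph in section I (Research Plan) of the protocol is repeated unchanged in section I of the SAP. It borrows *Bacteroides/Prevotella* means and SDs of "26.3 ± 13.2 and 14.8 ± 15.1 in the low-frailty and high-frailty groups" from a cited study, says these "yield an effect size of 0.81", and describes that as "a value that is sufficient to obtain 80% power at a type-I error probability of 0.05 with a study sample size of 40 subjects". The test and its sidedness are not given. The opening paragraph of the same section fixes the allocation: the HF and LF "groups will each contain 20 subjects (10 men, 10 women").

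The comparisons this sample size has to serve appear in both documents under the heading on bacterial taxa that differentiate HF from LF older adults. One asks "if the overall gut microbial profile in HF is significantly different when compared with LF older adults", using analysis of similarities on UniFrac distances at p ≤ 0.05. The other uses LEfSe "To identify bacterial taxa and relative abundance that are significantly different in HF when compared with LF older adults". Neither is given a direction.

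**The concern.** A power figure means little without the test and sidedness behind it. When the planned comparisons look for differences either way and a type-I error of 0.05 is quoted without comment, most readers will take it as two-sided. If the calculation was in fact one-sided, the advertised power is too high for the question being asked, and a null result would be read as stronger evidence of no difference than it is.

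The stakes are limited. The study calls itself a pilot (protocol section D) and assigns no treatment to participants. The point bears on how the sample size is justified and how negative findings are interpreted, not on whether the study can proceed.

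**Working it through.** **Inputs, all from section I.** Means 26.3 and 14.8; SDs 13.2 and 15.1; type-I error 0.05; 20 per group. The 40 are completers, so no dropout allowance applies.

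**Effect size.**
- Pooled SD = √[(13.2² + 15.1²)/2] = √[(174.24 + 228.01)/2] = 14.18.
- d = (26.3 − 14.8)/14.18 = 11.5/14.18 = 0.81, as stated.

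**Power of an unpaired t-test, 20 per group.** Degrees of freedom = 38. Noncentrality = d × √(n/2) = 0.81 × √10 = 2.56. Power is the probability that a noncentral t with these parameters exceeds the critical value; the two-sided version adds the opposite tail, which is negligible here.

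| Test at 0.05 | Critical t (38 df) | Power | Smallest n per group for 80% |
|---|---|---|---|
| One-sided | 1.686 | 80.8% | 20 (exact solution 19.6; 19 gives 78.9%) |
| Two-sided | 2.024 | 70.4% | 25 (24 gives 78.4%, 25 gives 80.1%) |

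So 20 per group is exactly the smallest one-sided sample size. A simulation of 100,000 pairs of normal samples with the stated means and SDs, analysed by a two-sided pooled t-test, gave 70.5%.

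**Other two-sided tests of two independent groups, 20 per group.**
- Normal approximation: 72.6% (needs 24 per group, 48 in total).
- Mann-Whitney, simulated with normal data: 67.5%.
- Fisher z on the equivalent correlation, r = 0.81/√(0.81² + 4) = 0.375, n = 40: 67.0%.

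None reaches 80%.

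**What two-sided 80% would need.**
- With 20 per group at 0.05: d = 0.909, or 0.909 × 14.18 = 12.9 percentage points, against the 11.5 used for planning.
- With d = 0.81 at 0.05: 25 per group, 50 in total.
- With d = 0.81 and 20 per group: a two-sided type-I error of 0.094, nearly twice the stated 0.05.

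**The mouse power statement.** The AIM 2 claim (effect size 2.6, 12 donors, 99% power) gives 99.4% one-sided and 98.1% two-sided at 6 donors per group. The gap is too small to prove anything alone, but it also sits closer to a one-sided calculation.

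**The case against.** The best reply is that nothing was miscalculated: effect size, power and sample size agree under one standard test, and what is missing is a label. It is true that the figures agree. But a one-sided setting is a substantive choice, and it has to match the hypotheses. No one-sided hypothesis is declared, and the HF/LF comparisons have no direction. The borrowed means do differ in a known direction, but a planning input is not a hypothesis.

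A second reply is that no HF/LF t-test is planned, so 70% is not the power of any planned analysis. This stands as a limit on what the 70% means. It applies equally to the 80%, which is also a single-taxon figure, so the corrected statement should carry the caveat.

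A third is that matching or adjustment could recover the power. Two-sided power would be about 80% if 20 matched pairs had a within-pair correlation near 0.25, and 79.7% if covariates explained 20% of the variance. These values are assumptions that the documents do not make. The matching described (section I, and exclusion criterion xx in protocol section A) is of groups, and diet is recorded, but no paired or covariate-adjusted HF/LF test is specified.

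Finally, for a pilot whose sample size will not change, this may look minor. That limits the consequence, but the plan does give a numerical power, and it should be right as readers will take it.

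**Conclusion.** The concern holds. For an unpaired, unadjusted comparison of one taxon at two-sided 0.05, 20 per group gives about 70% power for the planning effect of 0.81, not 80%. The chance of missing that effect is about 30% rather than 20%. The stated 80% needs a one-sided test that neither document declares and that does not fit the non-directional HF/LF comparisons.

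The 70% takes the cited means and SDs at face value and assumes roughly normal data and no gain from matching or covariates. It does not describe the power of the analysis of similarities or LEfSe, for which the documents give no figure. The statement should be corrected; the design can stand.

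**What to change.** Keep 40 subjects and replace the power claim in section I of both documents with wording such as:

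> With 20 per group, a two-sided 0.05 two-sample t-test on a single taxon has about 70% power for an effect size of 0.81 and 80% power for 0.91. This t-test is a planning approximation and is not the power of the analysis of similarities or LEfSe.

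If a one-sided test was intended, say so, state the direction and the reason for it, and reconcile it with the HF/LF comparisons, which currently have none. If 80% two-sided power at 0.81 is wanted, the target becomes 50 completers.

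The restatement costs one or two sentences in each document and a less favourable power figure. It adds no subjects and changes no analysis.
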